6.1 Information to be collected on Screening failures

Patients may discontinue from the study prior to randomization. These patients are considered Screening failures.

If a patient discontinues before entering the double-blind treatment period at baseline, the IRT must be notified within 2 days and the reason for not being randomized will be entered on the Screening Phase Disposition eCRF page.

In addition, only demography data, the reason for failing (screening failure log) and informed consent will be collected for those patients who fail to enter the treatment phase.

Reporting of potential SAE which may have occurred from time of signing informed consent until screening failure time should be followed as described in Section 7.2

6.2 Patient demographics/other baseline characteristics

Patient demographic and baseline characteristics data to be collected on all patients and to be recorded in the eCRF include:

- Year of birth, age, sex, race and source of patient referral
- Relevant AS and general medical history/current medical condition data until the start of study treatment, number of previous DMARDs used, date of diagnosis of AS, previous AS therapies, functional status class according to the New York criteria, cardiovascular medical history and smoking history

Whenever possible, diagnoses and not symptoms will be recorded.

6.3 Treatment exposure and compliance

All dates and times of study treatment administration will be recorded on the appropriate Dosage Administration Record eCRF page.

Drugs administered prior to start of treatment and other drugs continuing or started during the study treatment period will be entered in the Prior/Concomitant medications or Significant non-drug therapies eCRF page.

Compliance is expected to be 100%, unless temporary interruption is needed for safety reasons as described in (Section 5.5.5). Compliance will also be assessed by a Novartis/CRO monitor using information provided by the authorized site personnel.

6.4 Efficacy

- Assessment of Spondyl Arthritis International Society criteria (ASAS)20
- ASAS-NSAID score
- Patient's global assessment of disease activity (VAS)
- Patient's assessment of back pain intensity (VAS)
- Bath Ankylosing Spondylitis Functional Index (BASFI)
- Bath Ankylosing Spondylitis Disease Activity Index (BASDAI)
- Spinal mobility assessed by Bath Ankylosing Spondylitis Metrology Index (BASMI)

hsCRP and ESR

6.4.1 Assessment of ASAS-NSAID score

The ASAS-NSAID score will be calculated in accordance with the ASAS recommendations (Dougados et al 2011). NSAID intake will be collected in accordance with the ASAS recommendations (i.e., name, mean dose, number of days of intake during a period of time). Thereafter, the ASAS-NSAID score will be calculated considering both the daily dose of the specific NSAID(s) and the percentage of days of intake of the NSAID(s) during a given period of time.

Detailed information for calculating the ASAS-NSAID score is given in Appendix 4.

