From Week 16 on, those patients originally randomized to placebo will self-inject Secukinumab 150 mg at weeks 17, 18, 19 and 20, while patients originally randomized to either of the Secukinumab groups will receive their next Secukinumab injection after Week 16 at Week 20 with Placebo injections at weeks 17, 18, 19 to maintain the blinding of the treatment assignment for the secondary / exploratory endpoint analyses.

Patients will be asked to capture NSAID intake and level of AS neck, back and hip pain (BASDAI question 2; see Appendix 4) on a daily basis in a patient diary. Guidance will be

provided to patients that NSAID intake should be reduced upon an improvement in back pain and that the reduction should preferably happen step-wise and instead of an abrupt stop of any NSAID intake. However, deviance from this guidance will be acceptable and may be discussed between investigator and patient. Patients may deviate from this guidance if required, e.g. NSAID use necessary for non-spinal pain (e.g. entheses, peripheral joints, and headache). Also, if pain levels increase, patients may increase NSAID usage on an on-demand basis. The reduction in NSAID intake will be assessed using the ASAS-NSAID score (Dougados et al 2012).

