4.1 Inclusion criteria

Patients eligible for inclusion in this study have to fulfill **all** of the following criteria:

- 1. Patient must be able to understand and communicate with the investigator and comply with the requirements of the study and must give a written, signed and dated informed consent before any study assessment is performed
- 2. Male or non-pregnant, non-lactating female patients at least 18 years of age
- 3. Diagnosis of active AS with prior documented radiologic evidence (X-ray or radiologist's report) fulfilling the Modified New York criteria for AS (Appendix 3)

- 4. Active AS assessed by total BASDAI \geq 4 (0-10) at baseline
- 5. Spinal pain as measured by BASDAI Question $2 \ge 4$ cm on a 0-10 cm numeric rating scale at baseline
- 6. Total back pain as measured by VAS \geq 40 mm (0-100 mm) at baseline
- 7. Patients should have been on at least 2 different NSAIDs at the highest recommended dose for at least 4 weeks in total in the past, prior to randomization, with an inadequate response or failure to respond, or less if therapy had to be reduced due to intolerance, toxicity or contraindications
- 8. Patients must report regular intake of NSAIDs of at least 50% of the highest recommended dose at Screening. Patients with prior TNFα inhibitor therapy must report regular intake of NSAIDs of at least 50% of the highest recommended dose at baseline after the appropriate washout
- 9. Patients are required to be on a stable dose of NSAIDs for at least 2 weeks before randomization
- 10. Patients who have previously been on a TNF α inhibitor will be allowed entry into study after an appropriate wash-out period prior to randomization:
 - 4 weeks for Enbrel® (etanercept) with a terminal half-life of 102 ± 30 hours (s.c. route)
 - 8 weeks for Remicade® (infliximab) with a terminal half-life of 8.0-9.5 days (i.v. infusion)
 - 10 weeks for Humira® (adalimumab) with a terminal half-life of 10-20 days (average 2 weeks) (s.c. route)
 - 10 weeks for Simponi[®] (golimumab) with a terminal half-life of 11-14 days
 - 10 weeks for Cimzia[®] (certolizumab) with a terminal half-life of 14 days

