13.4.1 Analysis and report of NSAID intake during clinical trials/studies

1. As soon as the information contained in Table 13-4 is available (eg, name, mean dose, number of days of intake during a period of time), the recommendation is to analyse/report the data in terms of NSAID equivalent dose in mg/day on a 0–100 scale. The 150 mg equivalent diclofenac is set to 100. When the exact number of days with NSAID intake is not known (usually when the interval of time between 2 visits exceeds 2 weeks), it is recommended to refer to the semi-quantitative estimation summarised in Table 13-4. In this case, a score of 7/7 is proposed for the answer 'every day', 6/7 for >5 days/week, 4/7 for >3 to ≤5 days/week, 2 for >1 to ≤3 days/ week, 0.5 for ≤1 day/week and 0 if the patient did not take any NSAID during the study period (Dougados et al 2011).

The general formula for the calculation is:

(equivalent NSAID score) × (days of intake during period of interest) × (days per week)/(period of interest in days)

 $^{^{\}mathrm{a}}$ Elevated ALT/AST > 3 × ULN and TBL > 2 × ULN but without notable increase in ALP to > 2 × ULN

Page 73

For example, if during a period of interest (between 2 visits) of 6 months, the patient has taken piroxicam 20 mg during 4 months and if during this 4-month period he has taken piroxicam 3–5 days per week the calculation is as follows:

100 (20 mg piroxicam score) \times 120 (4 months) \times 4/7 (3–5 days/week)/180 (6 months) = 38.1

If the patient has used 10 mg piroxicam during the remaining 2 months on 2 days a week, the NSAID score for this period is:

50 (10 mg piroxicam score) \times 60 (2 months) \times 2/7 (1–3 days/week)/180 (6 months) = 4.8 In this example the total score for the 6 month period is 42.9 (38.1 plus 4.8).

Table 13-4 ASAS recommendations for the approach to collection of NSAID intake for use in clinical trials/epidemiological studies of spondyloarthritis

NSAID intake si	nce the last visit	Yes □	No □	
NSAID name	Average daily intake	Days with intake	Starting date	Ending date
	III mg	<pre> <1 day/week</pre>	 	IIIIIII Ongoing

- 27. When the name and the dose of the NSAID intake are not available but the number of days with NSAID intake is available, the recommendation is to present the results as the percentage days with at least NSAID intake during a period of time.

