### 2.2.1 Subgroup of interest

Summary of the primary variable will also be presented by the below subgroups:

- ASAS-NSAID
  - Lower user groups (baseline score <75)
  - Higher user group (baseline score  $\geq$ 75)
- Gender
  - Male
  - Female

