### 5.5.7 ASAS-NSAID Score

The recommendations by ASAS (Dougados 2010) will be used to score each patient's NSAID use during specific time periods. The components that go into the calculation of the score is the type of NSAID, average daily dose, length in days of the time period of interest and the number of days with NSAID intake within the time period of interest. The final score should be between 0 and 100 but can in rare cases be larger than 100.

The scoring of NSAIDs is described below.

Score	Intake
0	No intake
100	150 mg diclofenac, 600 mg etodolac, 150 mg indometacin, 20 mg piroxicam, 1000 mg naproxen, 90 mg etoricoxib, 200 mg ketoprofen, 20 mg tenoxicam, 200 mg aceclofenac, 200 mg flurbiprofen, 15 mg meloxicam, 400 mg celecoxib, 2400 mg ibuprofen, 400 mg phenylbutazone.

The CRF provided dose information will be handled as follows:

- Doses > maximum dose will be scored as > 100
- Missing doses will be scored with maximum daily dose for the current NSAID (i.e. score of 100)

Drug start and end dates are needed in order to know the number of days an NSAID was prescribed. In case they are missing, the following rules will be used:

- Missing start dates will assume the start date of medication is Day -28 (i.e. prior to start of study drug)
- Missing end dates will assume the end date of medication is the patient's last day in the Study

- If the study drug is ongoing when the patient discontinues then the drug end date will be equal to the day of discontinuation. The period end date will also end on the day of discontinuation

The table below presents the score associated with the dosing frequency as specified by the ASAS definition and how the different database entries will be categorized. The frequency was not consistently specified in the ASAS publication, the below categorization was selected.

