**Table 5-2 Mapping of dosing frequency to NSAID score**

Frequency	Scores	Database entry
Patient did not take any NSAID during the period of interest	0/7	
<1 day/week	0.5/7	Q2W, MISSING, PRN, UNK, ASNEEDED, QM, Q4W, Q3W
≥1 – <3 days/week	2/7	Q1W, WEEKLY, BIW
≥3 – <5 days/week	4/7	TIW, QIW
≥5 – <7 days/week	6/7	
Everyday	7/7	TID, BID, DAILY, Q24H, QID, QD
Note: Q2W=every 2 weeks, PRN=as needed, UNK=unknown, Q1W=one a week, BIW=twice a week, TIW=three times a week, TID=three times a day, BID=twice a day, QIW= four times a week, Q24H=QID=QD=one a day, QM=one a month; Q4W=one every 4 weeks; Q3W=one every 3 weeks.		

To calculate the NSAID cumulative score the following formula will be used for each NSAID being taken:

$100 * (\text{Daily dose} / \text{pre-specified max dose}) * \text{frequency score} * (\text{min}(\text{medication end date, period end date}) - \text{max}(\text{medication start date, period start date}) + 1 = \text{range of days patient used the medication}) / \text{number of days the patient was in the period.}$

In case a patient takes more than one type of NSAID, changes the dose or the frequency of NSAID during the period of interest, additional scores will be calculated for each new combination and the final score for that patient is the sum of all scores.

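### SAP 5.5.7 scores a missing NSAID dose at the drug's maximum even when the patient's own dose is on record, which can hide or overstate dose reductions in the confirmatory ASAS-NSAID change

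*Protocol*

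**What the plan says.** **The score.** Protocol 6.4.1 says that "the ASAS-NSAID score will be calculated considering both the daily dose of the specific NSAID(s) and the percentage of days of intake". SAP 5.5.7 turns this into a product. It states: "To calculate the NSAID cumulative score the following formula will be used for each NSAID being taken". The formula is 100 × (daily dose / maximum dose) × frequency score × (days used / days in the period), summed over NSAIDs.

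**Missing items.** For the dose, SAP 5.5.7 says: "Missing doses will be scored with maximum daily dose for the current NSAID (i.e. score of 100". It makes no exception by visit, or for a patient with a recorded dose of the same drug. For the frequency, SAP Table 5-2 gives a score of 0.5/7 to these entries: "Q2W, MISSING, PRN, UNK, ASNEEDED, QM, Q4W, Q3W".

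**Doses to be expected.** The entry floor in Protocol 4.1 is: "Patients must report regular intake of NSAIDs of at least 50% of the highest recommended dose at Screening". Protocol 3.1 advises all patients to stay on the maximum recommended or tolerated dose for the first 4 weeks and to taper or stop from Week 4. On-demand use is allowed, and the guidance is that "the reduction should preferably happen step-wise and instead of an abrupt stop of any NSAID intake".

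**Use of the score.** The change from baseline at Week 12 is H2 (pooled arms), H7 (delayed tapering) and H8 (early tapering) in SAP 2.7.2. If H2 is not rejected, H3 to H11 become exploratory. SAP 2.7.3 deals with missing binary variables and SAP 2.5.4 with the primary analysis. Neither provides a sensitivity analysis for the dose rule.

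**The concern.** The rule puts the largest ordinary dose into a trial in which half-dose patients may enter and every patient is advised to reduce after Week 4. The mixed model then treats the inserted value as observed.

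The error has no fixed direction. After Week 4 the maximum hides a dose reduction. At baseline it creates or enlarges one, and baseline score is also a covariate in the model. The rule therefore cannot be defended as uniformly conservative.

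It also ignores better information, since a patient's own recorded dose of the same drug is not used. It runs against the neighbouring rule as well: a missing dose goes to the top of its scale, while a missing frequency goes close to zero.

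Missing doses are foreseeable. Protocol Table 6-1 has intake reported in the eCRF up to Week 4 and in a patient diary afterwards. Protocol 8.3 says the diary is on paper and is entered by study staff. The rate of missing doses may therefore differ between baseline and Week 12.

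**Working it through.** **1. Reproducing the plan's figures.** The example in Protocol 13.4.1 reproduces: 100 × 120 × (4/7) / 180 = 38.1 and 50 × 60 × (2/7) / 180 = 4.8, total 42.9.

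Protocol 9.7 assumes reductions of 63.9 and 36.6 (difference d = 27.3) with SD 40, and claims more than 90% power for each secukinumab group. With power = Φ(d / (SD × √(1/n₁ + 1/n₂)) − 1.96):
- 62 per group: 27.3 / 7.184 = 3.80, power 96.7%. This agrees with the claim.
- Pooled H2 with 190 patients at 2:1 (127 vs 63): 27.3 / 6.164 = 4.43, power 99.3%.

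**2. Effect on one record.** True half dose, used throughout the period:

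| Frequency score | True score (50 × f) | Score with dose missing (100 × f) |
|---|---|---|
| 7/7 | 50 | 100 |
| 6/7 | 42.9 | 85.7 |
| 4/7 | 28.6 | 57.1 |
| 2/7 | 14.3 | 28.6 |
| 0.5/7 | 3.6 | 7.1 |

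The score doubles in every row but reaches 100 only for daily use over the whole period. A record with both dose and frequency missing scores 7.1.

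**3. Effect on one patient's change (daily use).**
- Baseline 100, Week 12 half dose with the dose missing: true 50 − 100 = −50; SAP 100 − 100 = 0.
- Baseline half dose recorded, Week 12 quarter dose with the dose missing: true 25 − 50 = −25; SAP 100 − 50 = +50.
- Baseline half dose with the dose missing, Week 12 quarter dose recorded: true −25; SAP 25 − 100 = −75.

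**4. Effect on the arms.** The documents give no missing-dose rate, so a share m of 2% to 20% is assumed. Each affected Week 12 score is set to 100 (the upper bound for one drug) and SD stays at 40. With an equal share m of patients in all arms, the difference becomes (1 − m) × 27.3:

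| m | Difference | Power, 62 per group | Pooled H2 power |
|---|---|---|---|
| 2% | 26.8 | 96.1% | 99.1% |
| 5% | 25.9 | 95.1% | 98.8% |
| 10% | 24.6 | 92.8% | 97.9% |
| 20% | 21.8 | 86.0% | 94.3% |

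For unequal missingness a baseline mean is needed; 100 is assumed, so the true Week 12 means are 36.1 (secukinumab) and 63.4 (placebo).
- Secukinumab arms only, m = 10%: 63.4 − (0.9 × 36.1 + 10) = 20.9, pooled power 92.4%. At m = 20%: 63.4 − (0.8 × 36.1 + 20) = 14.5, pooled power 65.4%.
- Placebo only, m = 10%: (0.9 × 63.4 + 10) − 36.1 = 31.0. At m = 20%: (0.8 × 63.4 + 20) − 36.1 = 34.6. The effect is now overstated.

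A dose can be missing only where there is NSAID use, so equal missingness per record is not equal missingness per patient. For example, assume 80% users on placebo and 50% on secukinumab, a mean user score of 50 and 10% of doses missing. The shift is 0.1 × (0.8 × 50 − 0.5 × 50) = 1.5 points in favour of secukinumab.

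**5. Baseline.** If a share m of patients are half-dose daily users with a missing baseline dose, the mean baseline rises by 50m: 1.0, 2.5, 5.0 and 10.0 points at 2%, 5%, 10% and 20%.

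**The case against.** **There is no breach of the protocol.** A reader might infer that the SAP contradicts Protocol 13.4.1 and should have declared a change in its section 4. That recommendation applies under this condition: "When the name and the dose of the NSAID intake are not available but the number of days with NSAID intake is available". It needs both name and dose to be absent. SAP 5.5.7 covers a known drug with an unknown dose, for which the protocol gives no rule. The SAP fills a gap. This objection stands.

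**The patient is not always scored as fully dosed.** A reader might infer a total of 100 for anyone with a missing dose. Only the dose factor is 100. Less-than-daily intake is one of the main ways to taper here, and such patients score lower. This also stands.

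**The maximum is plausible early on.** Protocol 3.1 advises the maximum recommended or tolerated dose up to Week 4. This stands for that phase, but it does not justify overriding a patient's recorded lower dose.

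**Few doses may be missing.** Eligibility depends on a known and stable dose (Protocol 4.1, criteria 8 and 9), and adherence to the entry criteria is fully verified (8.1). The diary is checked at Weeks 6, 8, 12, 16 and 20 (Table 6-1), and incomplete data are queried (8.3). This makes a missing baseline dose in particular less likely. It does not show that the rate is zero, and the SAP itself foresees missing doses.

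**Carrying a dose has faults too.** A dose from before Week 4 carried forward can hide a taper, and a tapered dose carried back to baseline can erase a real reduction. This is right, and any replacement rule must not cross Week 4.

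**Conclusion.** The concern holds as a criticism of an SAP imputation rule. The maximum is inserted where the patient's own dose may be known, the error can go in either direction, and three confirmatory hypotheses use the result without a planned sensitivity analysis.

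The effect is probably modest. With doses missing equally across arms, pooled H2 power stays at about 94% or more up to 20% missing, even with every imputed score set to 100. At 20%, pairwise power (H7, H8) falls to 86.0%, below the plan's stated level of more than 90%.

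A reader might infer that the gate at H2 is in serious danger. That needs a large imbalance, such as 20% missing in the secukinumab arms only, and nothing in the documents supports one. Bias in favour of secukinumab is equally possible and equally unsupported.

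The arm-level figures rest on an assumed missing share and an unchanged SD of 40; the one-sided cases also assume a baseline mean of 100. The doubling of a half-dose record needs none of these assumptions.

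A lesser consequence concerns SAP 2.2.1, whose lower stratum is "Lower user groups (baseline score <75". A daily user with a missing baseline dose goes into the other stratum automatically. Only a summary of the primary variable is planned there, so this matters little.

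**What to change.** Replace the missing-dose bullet in SAP 5.5.7 with a rule of this kind, before unblinding:

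- A missing dose is scored with the same patient's nearest recorded dose of that NSAID within the same phase. For baseline and up to Week 4, only records up to Week 4 are used. After Week 4, the last recorded dose before the gap is used, otherwise the first after it, without going back before Week 4.
- The drug's maximum is used only if no such dose is recorded.
- The number of imputed doses is reported by arm and visit.
- The present maximum-dose rule is kept as a sensitivity analysis for H2, H7 and H8.

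The cost is a short SAP change, a small change to the derivation program, one count table and one repeat of the model. The downside is that a carried dose may be out of date in some patients and may still understate a taper. Where the recorded dose is at or below the maximum, it understates it by no more than the present rule does.

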6.4.2 Assessment of SpondyloArthritis International Society criteria (ASAS)

The ASAS response measures consist of the following assessment domains (Sieper 2009). The main ASAS domains are as follows:

- 1. Patient's global assessment of disease activity measured on a VAS scale
- 2. Patient's assessment of back pain, represented by either total or nocturnal pain scores, both measured on a VAS scale
- 3. Function represented by BASFI average of 10 questions regarding ability to perform specific tasks as measured by VAS scale
- 4. Inflammation represented by mean duration and severity of morning stiffness, represented by the average of the last 2 questions on the 6-question BASDAI as measured by VAS scale

The additional assessment domains are as follows:

- 5. Spinal mobility represented by the BASMI lateral spinal flexion assessment
- 6. C-reactive protein (acute phase reactant)

Investigator must review the results timely and document adverse events, if applicable.

ASAS Response Criteria-20% (ASAS20)

ASAS20 response is defined as an improvement of $\geq 20\%$ and ≥ 1 unit on a scale of 10 in at least 3 of the 4 main domains and no worsening of $\geq 20\%$ and ≥ 1 unit on a scale of 10 in the remaining domain.

6.4.2.1 ASAS Response Criteria-40% (ASAS40)

ASAS40 response is defined as an improvement of \geq 40% and \geq 2 units on a scale of 10 in at least three of the four main domains and no worsening at all in the remaining domain.

6.4.2.2 ASAS 5/6 improvement criteria

The ASAS 5/6 improvement criteria is an improvement of \geq 20% in at least five of all six domains.

6.4.2.3 ASAS partial remission criteria

The ASAS partial remission criteria are defined as a value not above 2 units in each of the four main domains on a scale of 10.

Page 43 Protocol No. CAIN457FDE03

6.4.3 Patient's global assessment of disease activity (VAS)

The patient's global assessment of disease activity will be performed using a 100 mm visual analog scale (VAS) ranging from not severe to very severe, after the question, "How active was your disease on average during the last week?".

6.4.4 Patient's assessment of back pain intensity (VAS)

The patient's assessment of back pain will be performed using a 100 mm VAS ranging from no pain to unbearable pain, after the question "Based on your assessment, please indicate what is the amount of back pain at any time that you experienced during the last week?" and "Based on your assessment, please indicate what is the amount of back pain at night that you experienced during the last week?"

